9.1. Adverse Events

A pretreatment event is defined as any event that occurs prior to administration of any study treatment; it does not necessarily have to have a causal relationship with study participation. A treatment emergent adverse event (TEAE) is defined as any event temporally associated with the use of a product whether or not considered related to the use of the product. Adverse event (AE) verbatim reported terms will be coded by SOC and PT using the latest version of MedDRA.

For the purpose of inclusion in AE summaries/analyses, incomplete start and stop dates will be imputed as follows:

Missing start dates will be handled as follows (where UK, UKN and UNKN indicate unknown or missing day, month and year respectively):

- UK-MMM-YYYY: if MMM and YYYY are the same as that of 1st dose, then impute to same date as 1st dose; otherwise impute to 01-MMM-YYYY;
- DD-UNK-YYYY; if DD and YYYY are the same as that of 1st dose, then impute to same date as 1st dose; otherwise impute to DD-JAN-YYYY;
- DD-MMM-UNKN; if DD and MMM are the same as that of 1st dose, then impute to same date as 1st dose; otherwise impute to DD-MMM-YOSCR, where YOSCR is year subject was initially screened;
- UK-UKN-YYYY: if YYYY is the same as that of 1st dose, then impute to same date as 1st dose; otherwise impute to impute to 01-JAN-YYYY;
- UK-MMM-UNKN: if MMM is the same as that of 1st dose, then impute to same date as 1st dose; otherwise impute to 01-MMM-YOSCR, where YOSCR is year subject was initially screened;
- DD-UNK-UNKN: if DD is the same as that of 1st dose, then impute to same date as 1st dose; otherwise impute to impute to DD-JAN-YOSCR, where YOSCR is year subject was initially screened;
- UK-UKN- UNKN: impute to date of subject's 1st dose.

If the imputed start date is after the raw stop date, then the imputed start date will be set as the same as the stop date.

Missing stop dates will be handled as follows (where UK, UKN and UNKN indicate unknown or missing day, month and year respectively):

- UK-MMM-YYYY: impute to the last day of the month;
- DD-UNK-YYYY: impute to DD-DEC-YYYY;
- DD-MMM-UNKN: impute to DD-MMM-YOLV, where YOLV is year of subject's last study visit;
- UK-UKN-YYYY: impute to 31-DEC-YYYY;
- UK-MMM-UNKN: impute to LD-MMM-YOLV, where LD is the last day of MMM and YOLV is year of subject's last study visit;
- DD-UNK-UNKN: impute to DD-DEC-YOLV, where YOLV is year of subject's last study visit;
- UK-UKN- UNKN: impute to day of subject's last study visit.

If the imputed stop date is before the raw or imputed start date, then the imputed stop date will be set as the same as the start date.

AE duration will be calculated as (Stop Date – Start Date) + 1.

AE summary tables will include numbers and percentages of subjects experiencing at least one event by treatment arm. The following is a list of AE summary tables to be generated:

- Overview of AE, AE with onset within 28 days/7 days after study treatment
- TEAEs, TEAEs with onset within 28 days/7 days after study treatment by SOC and PT
- TEAEs, TEAEs with onset within 28 days/7 days after study treatment by Dose Number, SOC and PT
- TEAEs, TEAEs with onset within 28 days/7 days after study treatment by Dose Number, CTCAE Grade, SOC and PT
- Serious TEAEs by Dose Number, SOC and PT
- TEAEs, TEAEs with onset within 28 days/7 days after study treatment by Dose Number, Relationship to IP and EP, SOC and PT
- Serious TEAEs, serious TEAEs with onset within 28 days/7 days after study treatment by Dose Number, Relationship to IP and EP, SOC and PT
- Grade >= 3 TEAEs, Grade >= 3 TEAEs with onset within 28 days/7 days after study treatment by Dose Number, SOC and PT
- Grade >= 3 TEAEs, Grade >= 3 TEAEs with onset within 28 days/7 days after study treatment by Dose Number, Relationship to IP and EP, SOC and PT
- TEAEs with Action of Study Treatment Held, TEAEs with Action of Study Treatment Held with onset within 28 days/7 days after study treatment by Dose Number, SOC and PT
- TEAEs with Action of Study Treatment Permanently Discontinued, TEAEs with Action of Study Treatment Permanently Discontinued with onset within 28 days/7 days after study treatment by Dose Number, SOC and PT

Additional AE/SAE summary tables may be added as appropriate.

A subject with 2 or more different adverse events within the same level of the MedDRA term and regimen will be counted only once in that level using the most extreme incident (most severe for the intensity analyses, and related for the relationship to study drug analyses). For the AE with missing relationship to drug/procedure will be imputed as related. TEAEs by dose will be counted by the AE onset date not earlier than the date of treatment and earlier than the subsequent treatment for the first dose and second dose, and any AEs with onset date on or later than the third dose will all be counted to the third dose.

Data listings will be provided for AE, SAE, TEAE leading to treatment discontinuation, TEAE with CTCAE Grade >=3, TEAE with onset within 28 days/7 days after study treatment, and AEs resulting in death separately.

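### Four of the seven onset-date rules for adverse events can place a post-dose event before first dose, and the missing-day rule ignores doses 2 and 3

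*SAP*

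**What the plan says.** Section 9.1 gives the imputation a direct role in the tables: "For the purpose of inclusion in AE summaries/analyses, incomplete start and stop dates will be imputed as follows". It then lists seven onset patterns.

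- Day missing (UK-MMM-YYYY): "if MMM and YYYY are the same as that of 1st dose, then impute to same date as 1st dose; otherwise impute to 01-MMM-YYYY".
- Month missing (DD-UNK-YYYY): if day and year match, "then impute to same date as 1st dose; otherwise impute to DD-JAN-YYYY".
- Year missing (DD-MMM-UNKN): the first-dose date if day and month match, "otherwise impute to DD-MMM-YOSCR, where YOSCR is year subject was initially screened".
- Day and month missing (UK-UKN-YYYY): "if YYYY is the same as that of 1st dose, then impute to same date as 1st dose", otherwise 1 January of the recorded year.
- Day and year missing (UK-MMM-UNKN): the first-dose date if the month matches, otherwise the first of that month in the screening year.
- Month and year missing (DD-UNK-UNKN): the first-dose date if the day matches, otherwise January of the screening year.
- Everything missing: the first-dose date.

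The only later correction pulls an imputed onset back to the recorded stop date if it would fall after it. Classification then depends on the onset date: "A pretreatment event is defined as any event that occurs prior to administration of any study treatment". For the dose tables, "TEAEs by dose will be counted by the AE onset date not earlier than the date of treatment". Section 9.1.2 compares the arms on events within 28 days of any dose, and repeats this for 7 days and for the whole study.

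**The concern.** An onset date that could lie after first dose should not be placed before it by default. The January and screening-year defaults do this whenever the known parts do not happen to match first dose. The rules are also inconsistent with each other: a date with a known day can become pretreatment while a date with nothing but the year stays post-dose. Elsewhere Section 9.1 imputes a missing relationship to treatment as related, so the plan's approach to missing safety data is otherwise cautious.

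The missing-day rule is a separate matter. It checks the month of dose 1 only, although doses are given at Day 0, Week 4 and Week 12 (Section 3.3). A reaction just after dose 2 or 3 can therefore be dated before that dose. At stake are the treatment-emergent tables, the tables by dose number, and secondary endpoint 1a (Section 3.2.2), which covers events 7 and 28 days after each treatment.

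**Working it through.** The SAP states no figure for this point, so there is none to reproduce. The check applies the rules as written.

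**Worked example.** First dose 20-JUN-2018, screened in 2018. Adding 28 and 84 days gives dose 2 on 18-JUL-2018 and dose 3 on 12-SEP-2018.

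| Recorded onset | True onset | Imputed | Result |
|---|---|---|---|
| 10-UNK-2018 | 10 Aug 2018 | 10-JAN-2018 | 161 days before first dose: pretreatment |
| UK-UKN-2018 | 10 Aug 2018 | 20-JUN-2018 | day of first dose: post-dose |
| 15-MAR-UNKN | 15 Mar 2019 | 15-MAR-2018 | 97 days before first dose: pretreatment |
| UK-JUL-2018 | 19 Jul 2018 (1 day after dose 2) | 01-JUL-2018 | credited to dose 1, 11 days after it |
| UK-SEP-2018 | 14 Sep 2018 (2 days after dose 3) | 01-SEP-2018 | credited to dose 2, 45 days after it: outside every 28-day window |
| UK-AUG-2018 | 20 Aug 2018 (33 days after dose 2) | 01-AUG-2018 | 14 days after dose 2: moved into a 28-day window |

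**Pretreatment share.** Assumptions: first dose uniform over one calendar year, screening 1 to 70 days earlier, true onset uniform over 88 weeks (88 × 7 = 616 days), no help from a stop date. Share of truly post-dose onsets dated before first dose:

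- DD-UNK-YYYY: 26% over all onsets, and about 88% when onset is in the calendar year of first dose
- DD-MMM-UNKN: 53%
- UK-MMM-UNKN: 50%
- DD-UNK-UNKN: 96%
- UK-MMM-YYYY, UK-UKN-YYYY and all missing: 0%

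The year-missing figures depend on the screening lag. With a fixed lag of 70 days, DD-MMM-UNKN rises to about 62% and UK-MMM-UNKN to 58%.

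**Day missing, onset 0 to 7 days after dose 3.** The event stays with dose 3 only if the first of the onset month falls between the dose date and the onset. For onset j days after the dose that span has j + 1 days, so the chance is about (j + 1)/30.4. The mean of j + 1 over j = 0 to 7 is 4.5, and 4.5/30.4 = 14.8%. The remaining 85.2% are dated before dose 3. Enumerating every first-dose date in a year gives the same 85%, with 83% outside every 28-day window.

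**Day missing, onset 0 to 7 days after dose 2.** Again 85% are dated before dose 2, but none leaves every 28-day window, because the 28 days before dose 2 are the window of dose 1. They are credited to dose 1. Only about 34% remain within 7 days of any dose.

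**Net effect on the 28-day window.** Counting days 0 to 28 after each dose, the windows cover 29 + 28 + 29 = 86 days (day 28 is shared), so the true share is 86/616 = 14.0%. After imputation, the share within 28 days of any dose is:

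- UK-MMM-YYYY: 16.4%
- DD-UNK-YYYY: about 15%
- DD-MMM-UNKN: about 21%
- UK-MMM-UNKN: about 27%
- UK-UKN-YYYY: about 43%
- all missing: 100%
- DD-UNK-UNKN: about 4%

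**The case against.** A reader might infer that these rules always understate treatment-emergent and dose-related events. The SAP does not support that. Three branches send events to the day of dose 1: day missing in the first-dose month, day and month missing in the first-dose year, and everything missing. The first-of-month default also pulls late onsets into windows, and it is not the source of false pretreatment events: with a known year it never places a post-dose event before first dose. Under uniform onset, six of the seven patterns raise the share within 28 days of any dose. Some events that truly preceded dose 1 become treatment-emergent too, for example an onset on 5 June recorded as UK-JUN-2018 in the worked example.

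It is also fair to say that dose 2 events with only the day missing are re-attributed rather than lost from the any-dose 28-day comparison. A known day with an unknown month is an unusual pattern. Adverse events are assessed at every visit and call (Appendix 13.1), so badly incomplete dates near dosing should be rare. All collected data are listed (Section 4.4), and the rules are the same in both arms.

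All of this stands, and it limits the size and direction of the concern. It does not justify dating an event before first dose when its known parts allow a later onset, or keeping the less informative date as post-dose.

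**Conclusion.** The concern holds in two parts. First, the rules for DD-UNK-YYYY, DD-MMM-UNKN, UK-MMM-UNKN and DD-UNK-UNKN have no lower limit at first dose. They can turn post-dose events into pretreatment events, which then belong to no dose and drop out of the treatment-emergent tables. Second, UK-MMM-YYYY ignores doses 2 and 3, so most early reactions to dose 3 with the day missing leave every 28-day window, and those to dose 2 are credited mainly to dose 1.

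The net effect on 7- and 28-day counts is mixed in direction. Every percentage is conditional on the date being partial in the stated way and rests on the assumed spread of first doses, screening lags and onsets. The SAP does not say how many dates will be partial; the number is probably small. This is a faulty rule worth correcting, not evidence that the safety comparison is materially biased.

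**What to change.** Replace the onset rules in Section 9.1 with the following, applied in this order:

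1. Classify an event as pretreatment only if the known date parts or the stop date prove onset before first dose.
2. If month and year are both known and that month contains one or more doses, impute to the latest dose date in the month that is compatible with the known parts and the stop date.
3. Otherwise impute the earliest date on or after first dose that is compatible with the known parts and the stop date. Do not default a missing year to the screening year.

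In the worked example, if no stop date contradicts it, 10-UNK-2018 becomes 10-JUL-2018, 15-MAR-UNKN becomes 15-MAR-2019, UK-JUL-2018 becomes 18-JUL-2018, UK-SEP-2018 becomes 12-SEP-2018, and UK-UKN-2018 stays at 20-JUN-2018.

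The cost is a change of SAP wording and of one date-imputation program. The downside is that some events that truly preceded dose 1, or preceded a later dose in the same month, will be counted as treatment-emergent or credited to the later dose.

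### The imputed adverse-event start is checked only against a raw stop date, so some events that certainly ended before dose 1 are counted as dose 1 events

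*SAP*

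**What the plan says.** All the rules stand in SAP Section 9.1.

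- **Definition.** "A pretreatment event is defined as any event that occurs prior to administration of any study treatment".
- **Start, day and month missing.** "UK-UKN-YYYY: if YYYY is the same as that of 1st dose, then impute to same date as 1st dose; otherwise impute to impute to 01-JAN-YYYY".
- **Start, wholly missing.** "UK-UKN- UNKN: impute to date of subject's 1st dose".
- **Check on the imputed start.** "If the imputed start date is after the raw stop date, then the imputed start date will be set" equal to that stop.
- **Stop, day missing.** "UK-MMM-YYYY: impute to the last day of the month". The other stop rules likewise take the latest month, day or year.
- **Check on the imputed stop.** "If the imputed stop date is before the raw or imputed start date, then the imputed stop date will be set" equal to the start date.

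The section says that these imputations decide which events enter the summaries. Events are allocated to a dose by onset date, and an onset on the day of dose 1 counts to dose 1. A missing relationship is imputed as related. Section 9.1.2 compares the arms by risk difference for events with onset within 28 days, within 7 days, and over the whole study after any dose.

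**The concern.** The two checks are not symmetrical. The start check looks at a raw stop only; the stop check looks at a raw or imputed start. When both dates are partial, the dose 1 default for the start therefore prevails over whatever the recorded month or year of the stop shows.

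Setting an ambiguous onset to dose 1 is a sensible cautious rule. Here the timing relative to treatment is not ambiguous: the latest stop that the record allows is before any treatment. By the SAP's own definition the event is pretreatment, and the SAP would treat it so if the stop date were complete. Losing only the day of the stop reverses the classification.

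Such records can arise, because the schedule of events (Appendix 13.1) marks AE/SAE assessment at Screening, and that column's window reaches back 10 weeks relative to the biopsy. What is at stake is the accuracy of the dose 1, 7-day and 28-day tables, which describe tolerability, a secondary objective.

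**Working it through.** The SAP gives no figure on this point, so there is none to reproduce. The check applies the rules literally. All calendar dates below are assumptions.

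**Step 1. One record, with the stop partial and then complete.** Dose 1 on 20-JUN-2018, start recorded as UK-UKN-2018.

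| Step | Stop recorded UK-MAY-2018 | Stop recorded 20-MAY-2018 |
|---|---|---|
| Start imputed (year matches dose 1) | 20-JUN-2018 | 20-JUN-2018 |
| Start check against raw stop | no complete raw stop, so no change | start after stop, so start becomes 20-MAY-2018 |
| Stop imputed | 31-MAY-2018 | not needed |
| Stop check against raw or imputed start | stop before start, so stop becomes 20-JUN-2018 | not needed |
| Result | onset on day of dose 1, duration (20-JUN − 20-JUN) + 1 = 1 day | pretreatment |

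Gap between the latest possible stop and dose 1: 31-MAY to 20-JUN = 20 days.

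**Step 2. Which rule causes the misclassification.** The by-dose and 7/28-day tables use onset. Once the start has been set to dose 1 and the start check has not acted, the event is counted whatever happens to the stop. The stop reset changes only the derived stop and the duration; its effect is to remove the visible conflict.

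**Step 3. Which records are affected.** The rules were coded, and every event starting and stopping within an assumed 70 days before dose 1 was run through all 8 × 8 patterns of complete and missing date parts. Only records whose recorded stop parts rule out a stop on or after dose 1 were kept, with the last visit assumed to be 88 weeks after dose 1.

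Dose 1 on 15-JUN-2018, stop missing only its day. The qualifying days run from 6 April to 31 May, 25 + 31 = 56 days, giving 56 × 57 / 2 = 1596 start–stop pairs:

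- start missing day and month: 1596 of 1596 misclassified
- start wholly missing: 1596 of 1596
- start missing month only: 64 of 1596
- start missing month and year: 64 of 1596
- total 1596 + 1596 + 64 + 64 = 3320

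Dose 1 on 10-FEB-2018:

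- start wholly missing: 1891 of 1891 (stop missing its day), 465 of 465 (stop missing its month), 465 of 465 (stop missing day and month)
- start missing day and month, stop missing its day: 496 of 1891, because starts in 2017 do not match the dose year
- total over all patterns: 3458

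In both runs there was no misclassification when the start was complete, when the stop was complete, or when the start lacked only its day. These are counts of possible date patterns, not expected numbers of events.

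**Step 4. Test of the correction.** Comparing the imputed start with the raw or imputed stop, and setting the start to that stop when the stop is earlier, reduced 3320 to 0 and 3458 to 0.

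**Step 5. Size of the effect on the arm contrast.** Suppose a fraction q of subjects in each arm gains one false event, independently of true events. Each arm's proportion p becomes 1 − (1 − p)(1 − q), so the risk difference is multiplied by (1 − q). With q = 1/198 = 0.005, the relative attenuation is about 0.5%.

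**The case against.** **The word raw is not defined.** In Section 7.1 medication starts are not imputed, yet the comparison there is with the raw start, so raw may mean as recorded, including partial. On that reading UK-MAY-2018 precedes 20-JUN-2018 and the start check already works. This is possible, but Section 9.1 uses *raw* in one check and *raw or imputed* in the other, and a programmer following the text would take the contrast as intended.

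**The default to dose 1 is deliberately cautious.** True, and it should stay wherever the record leaves the timing open. It does not justify overriding a recorded month that settles the timing, and the SAP itself gives way when the stop is complete.

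**Few records will qualify.** The event must have an unknown start month but a stop known well enough to precede dose 1, and must arise in a short period with visits at Screening and Day 0. This stands, and it limits the point to a minor one.

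**The treatment-emergent definition sets no onset cut-off.** Also true, but the by-dose and 7/28-day tables do work from onset date.

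A reader might go further and infer any of the following. The SAP does not support them.

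- *Recorded stop dates are overwritten.* Only an imputed stop is moved. A complete stop is never moved, and Section 4.4 has all collected data listed.
- *Moving the stop is what makes the event treatment-emergent.* The tables count by onset; the start check is the cause.
- *Every pair of partial dates is affected.* A UK-MMM-YYYY start with a stop missing only its day is not. Nor is a wholly unknown start with a stop of UK-UKN-YYYY in the dose year, which is imputed to 31-DEC.

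**Conclusion.** The point holds as a minor error in a stated rule. Read literally, Section 9.1 assigns to the day of dose 1 an event whose recorded parts show that it ended earlier, when three conditions meet: the start lacks at least its month, its remaining parts match dose 1 (mainly "UK-UKN-YYYY: if YYYY is the same as that of 1st dose, then impute to same date as 1st dose", or a wholly unknown start), and the stop is partial but rules out dose 1. Each such event enters the dose 1 tables, the 7-day and 28-day tables and the Section 9.1.2 risk differences. It is also counted as related if relationship is missing.

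The number of such records cannot be derived from the SAP and is probably small. A reader might infer a material inflation of reactogenicity or dilution of the arm contrast; nothing in the document shows that, and the illustrative attenuation of about 0.5% suggests a slight effect. The efficacy analyses are untouched.

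The conclusion rests on reading raw as complete and not imputed. The worked dates, the 70-day pretreatment period and the 88-week last visit are assumptions; the logic of the worked example does not depend on the particular dates.

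**What to change.** In Section 9.1:

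1. State that the stop date is imputed first.
2. Extend the start check so that the imputed start is compared with the raw *or imputed* stop and set to that stop when it is later.
3. Keep the stop reset only for an imputed stop that precedes a raw, complete start. After step 2 an imputed start can no longer lie after the stop, so nothing else is needed.

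Deleting the stop reset alone would not help: the onset would stay on dose 1, and records with a stop before the start and a non-positive duration would appear.

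In the worked example the start becomes 31-MAY-2018 and the event stays pretreatment. The cost is a change of a few words in the SAP and a small change to the date-imputation program, with no new data.

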3.2.2. Secondary Endpoints

The secondary endpoints of this study are:

- 1. a. Incidence and severity of local and systemic events for 7 and 28 days following each investigational treatment and for the duration of the study (through Week 88 visit)
 - b. Incidence and severity of all adverse events including SAEs, SUSAR, UADE and other unexpected AEs for the duration of the study (through Week 88 visit)
- 2. Proportion of subjects with no evidence of cervical HSIL on histology (i.e. biopsies or excisional treatment) at Week 36 visit
- 3. Proportion of subjects with no evidence of HPV-16 and/or HPV-18 in cervical samples by type specific HPV testing at Week 36 visit
- 4. Proportion of subjects with no evidence of Low grade squamous intraepithelial lesion (LSIL) or HSIL (i.e. no evidence of CIN1, CIN2 or CIN3) on histology (i.e. biopsies or excisional treatment) at Week 36 visit

- 5. Proportion of subjects with no evidence of LSIL or HSIL (i.e. no evidence of CIN1, CIN2 or CIN3 on biopsies or excisional treatment) on histology (i.e. biopsies or excisional treatment) and no evidence of HPV-16 and/or HPV-18 by type specific HPV testing at Week 36 visit
- 6. Proportion of subjects with no progression of cervical HSIL to cervical carcinoma from baseline on histology (i.e. biopsies or excisional treatment) at Week 36 visit
- 7. Proportion of subjects who have cleared HPV-16 and/or HPV-18 on specimens from non-cervical anatomic locations (oropharynx, vagina and intra-anal) at Week 36 Visit
- 8. a. Levels of serum anti-HPV-16 and anti-HPV-18 antibody concentrations at Week 15 and 36 visits
 - b. Interferon-γ ELISpot response magnitudes at baseline, Weeks 15 and 36 visits
 - c. Flow Cytometry response magnitudes at baseline and Week 15 visits

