3.3. Treatments

A total dose of 6 mg VGX-3100 DNA has been selected for this study based on previous human experience with both the WFI/LGS and SSC formulations of VGX-3100, preclinical data with VGX-3100 and other DNA vaccines, and the safety and immunogenicity data generated in the HPV-001, HPV-003, and HPV-101 studies. In HPV-001 trial, the 6 mg dose was delivered IM followed by EP, which showed trends toward higher response rates and magnitudes of IFN-γ ELISpot responses compared to the low (0.6 mg) and mid-dose (2 mg) cohorts without significant safety issues [4]. The results

obtained in the phase 2 study suggest that the 6 mg dose was efficacious with an acceptable safety profile, therefore the 6 mg dose will also be evaluated in this Phase 3 trial.

Eligible subjects will receive a 3-dose series of either 6 mg (1 ml) VGX-3100 or Placebo by IM injection in the deltoid (or anterolateral quadriceps muscle as an alternate option, if deltoid muscle is not possible or appropriate) followed immediately by EP with the CELLECTRATM 5PSP. Study duration is approximately 88 weeks for each subject to finish 3 doses of treatment scheduled at Day 0, Week 4, and Week 12 study visit, and 76 weeks of long-term follow-up.

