9.1.1. Adverse Events of Special Interest

Adverse events of special interest (AESI) are the adverse events deemed related to VGX-3100/placebo delivered with CELLECTRATM 5PSP that require expedited communication from the Site to the Sponsor and meet any of the following criteria:

- Grade 3 or greater persistent administration site erythema, and/or induration recorded ≥ 2 hours immediately after Study Treatment
- Grade 4 or greater persistent administration site pain, tenderness recorded ≥ 2 hours immediately after Study Treatment
- Grade 3 or greater fever
- Grade 3 or greater systemic symptoms, including generalized pruritus

An AE summary table will include numbers and percentages of subjects experiencing at least one AESI by dose number, SOC and PT.

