- f At least 34 mL [4 x 8.5 mL yellow (ACD) tubes] whole blood per time point and 8 mL serum per time point at Screening, Day 0 and Week 8 (4 ml serum per time point at Week 15 and 36). A total of at least 68 mL of whole blood and 16 ml serum should be collected prior to dosing on Day 0.
- g At least 51 mL [6 x 8.5 mL yellow (ACD) tubes] whole blood and 4 mL serum should be collected at Week 15;
- h HPV genotyping and Pap smears are performed on the same ThinPrepTM cervical specimen;
- i Request that the subject abstain from sexual activity and refrain from use of douching or vaginal lubricants/medication for a period of 24 hours prior to cervical specimen collection;
- j Collected prior to the ThinPrepTM sample;
- k A photograph of the lesion with at least one attempt should done as follows: Acetic acid should first be applied to the cervix then photographs of the cervix and the associated lesion should be photographed prior to and after biopsies (if applicable) and at all colposcopic examinations; if repeat photographs are sought, they should be done at the next protocol-specified colposcopy visit.
- 1 Screening colposcopy is optional if adequate colposcopy was performed upon collection of initial biopsy;
- m Screening biopsy of the lesion should be collected as Paraffin-embedded cervical tissue, fresh cervical tissue, or H&E slides. Tissue to be analyzed for evidence of histopathologic regression will be obtained at Week 36 visit either by excision (e.g. LEEP, LLETZ, CKC) or by 4 Quadrant Biopsy or 4 Quadrant Biopsy with ECC based upon the assessment at Week 28 of cytology, HR HPV status, and colposcopic findings (See Tables 4 and 5);

- n Slides from biopsy and/or excised tissue must be reviewed by the PAC and residual cervical tissue from screening and/or Week 36 specimen(s) (paraffin blocks or unstained slides) may be used for immunohistochemistry (IHC) and HPV testing;
- o To be collected only if subject consents for intra-anal sample collection
- p One or both PRO questionnaires (i.e. SF-36 and EQ-5D-5L) will be completed by subjects enrolled in USA, Canada, Mexico, Germany and UK at multiple visits during the study. Additional quality of life questions will be asked at the Week 40 phone call. Refer to Section 6.8 for details
- q Activities at 8 to 14 days Post-Dose 3 phone call may be done at Week 15 if timing overlaps.

PPD Biostatistics and Programming

Statistical Analysis Plan (SAP) Client Approval Form

Client:	Inovio					

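### In the by-dose safety tables without a time window, dose 3 collects 76 of 88 weeks of adverse events, so the dose columns are not comparable; the serious-event table by SOC and PT is the main case

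*SAP*

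**What the plan says.** SAP section 9.1 gives the attribution rule in two parts. For doses 1 and 2, "TEAEs by dose will be counted by the AE onset date not earlier than the date of treatment and earlier than the subsequent treatment". For dose 3 there is no upper limit: "any AEs with onset date on or later than the third dose will all be counted to the third dose".

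Three other places determine how long that last interval is:

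- Section 3.3 describes "3 doses of treatment scheduled at Day 0, Week 4, and Week 12 study visit, and 76 weeks of long-term follow-up".
- Section 3.2.2 collects adverse events through the Week 88 visit.
- Section 9.1 defines a treatment-emergent event as "any event temporally associated with the use of a product whether or not considered related to the use of the product", with no end to the treatment-emergent period.

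The tables report numbers and percentages of subjects; section 9.1 mentions no person-time. It lists nine table entries by dose number. Eight are listed with 28- and 7-day onset versions beside the unrestricted one. The exception is "Serious TEAEs by Dose Number, SOC and PT". Section 9.1.1 adds a table of "numbers and percentages of subjects experiencing at least one AESI by dose number, SOC and PT", also without a window.

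The Week 36 procedure falls inside the dose 3 interval. Appendix 13.1, note m, says that tissue "will be obtained at Week 36 visit either by excision (e.g. LEEP, LLETZ, CKC) or by 4 Quadrant Biopsy", with or without endocervical curettage.

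**The concern.** A table by dose number invites comparison across its columns: is the third administration tolerated as well as the first? That comparison needs columns covering similar time after dosing. Here the dose 3 column covers far more time than the other two, and the entries are plain subject percentages. An event rate that never changes would still look like a sharp rise at dose 3.

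The long interval also mixes different kinds of event. A reaction to the third injection, an unrelated event a year later, and bleeding or infection after a Week 36 procedure all carry the same label. For patient-reported outcomes after Week 36, section 8.4 separates subjects with and without excision. The by-dose adverse event tables have no such split.

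The rule also leaves a gap. A subject who stops after dose 1 or dose 2 has no subsequent treatment, so nothing closes the interval for her last dose.

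What is at stake is how descriptive safety tables are read, above all the by-dose table of serious events.

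**Working it through.** **Inputs.** Doses at Weeks 0, 4 and 12 and 76 weeks of follow-up (section 3.3); adverse events to Week 88 (section 3.2.2); attribution rule (section 9.1). The SAP gives no adverse event rates, so the rates below are assumptions, shown as a range.

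**Step 1. The plan's own figure.** 88 − 12 = 76 weeks, which matches the follow-up stated in section 3.3.

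**Step 2. Attribution intervals.**

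- Dose 1: 4 − 0 = 4 weeks
- Dose 2: 12 − 4 = 8 weeks
- Dose 3: 88 − 12 = 76 weeks

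Dose 3 has 76/4 = 19 times the time of dose 1 and 76/8 = 9.5 times that of dose 2. Only 4/76 = 5% of it lies within 28 days of the injection. Weeks 36 to 88 make up 52/76 = 68% of it.

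**Step 3. Share of events under a constant background rate, no dose effect, full follow-up.** Share = interval / 88:

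- Dose 1: 4/88 = 4.5%
- Dose 2: 8/88 = 9.1%
- Dose 3: 76/88 = 86.4%

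This split does not depend on the rate assumed. Moving doses 2 and 3 and the last visit to the edges of their windows (±4 days, ±4 days, ±2 weeks) changes the dose 3 share only to between 73.4/86 = 85.4% and 78.6/90 = 87.3%.

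**Step 4. Share when some events are acute.** Let a fraction f of events be acute and dose-related, equal at each dose, and the rest background. Dose 3 share = f/3 + (1 − f) × 76/88:

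- f = 0: 86.4%
- f = 0.5: 0.167 + 0.432 = 59.8%
- f = 0.9: 0.300 + 0.086 = 38.6%
- f = 1: 33.3%

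**Step 5. What a serious-event table could show.** Percentage of subjects with at least one event = 1 − exp(−rate × weeks × 7/365.25), with assumed serious-event rates per subject-year and no dose effect:

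| Rate | Dose 1 | Dose 2 | Dose 3 |
|---|---|---|---|
| 0.01 | 0.08% | 0.15% | 1.45% |
| 0.02 | 0.15% | 0.31% | 2.87% |
| 0.10 | 0.76% | 1.52% | 13.55% |

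**Step 6. After the fix.** With 28-day windows each dose column covers 4 weeks on the nominal schedule, so background events in the dose columns split 4/12 = 33.3% each. Weeks 8 to 12 (4 weeks) and Weeks 16 to 88 (72 weeks) move to follow-up.

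**The case against.** The strongest reply is that the plan already supplies most of what is asked for. Eight of the nine by-dose entries in section 9.1 have 28- and 7-day versions, and one of these tabulates serious events by dose and relationship to the product and to electroporation. Listings cover serious events and events with onset within 28 or 7 days, and further tables may be added. This stands, and it limits the point to unwindowed output. A reader might infer that third-injection reactions cannot be separated from later follow-up and surgery. For nearly all by-dose output they can.

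A reader might also infer that AESIs will pile up at dose 3. The document does not support that. Section 9.1.1 requires an AESI to be deemed related to study treatment, and two of its four criteria concern administration-site reactions timed from the injection. The constant-background model therefore does not fit; the share should lie near the 33% end of Step 4. Related Grade 3 or greater fever or systemic symptoms could still be placed late, and the table has no window, but a large effect is not shown.

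A third inference is that the rule biases the comparison of VGX-3100 with placebo, because excision or biopsy is chosen from Week 28 findings that treatment may influence. The rule is identical in both arms. Any difference in surgical events would appear in any whole-study table, however doses are labelled, and its existence and direction presuppose an efficacy result. The risk differences in section 9.1.2 are taken after any dose and do not use by-dose attribution.

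Finally, the SAP does not say what the by-dose tables are for. That they will be read as a comparison across doses is an inference, though a natural one from their layout.

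**Conclusion.** The point holds for by-dose tables without a time window, chiefly serious events by SOC and PT, where no windowed counterpart is listed. There the dose columns cover 4, 8 and 76 weeks. Dose 3 collects about 86% of events under a constant background rate and about 60% if half of events are acute and dose-related. Events after the Week 36 procedure are included. These shares assume full follow-up and the nominal dosing schedule; the subject percentages also rest on assumed event rates.

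The AESI table lacks a window too, but no large distortion is demonstrated there. Efficacy results and between-arm risk differences are unaffected. Severity is minor, since only descriptive safety tables are involved. Because the rule is stated outright and yields percentages that cannot be compared across doses, and because changing it costs little, it is worth correcting as a cheap improvement.

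**What to change.** In the by-dose tables:

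- Attribute an event to a dose only if onset is on or after that dose, before the next dose, and within 28 days.
- Put every other post-dose event, meaning onset more than 28 days after the most recent dose received, whichever dose that was, in a separate follow-up column. This covers Weeks 8 to 12 and subjects who stop dosing early.
- Split follow-up at the first post-dose excision or biopsy, whenever it occurs, and distinguish excision from biopsy. Section 8.1 allows for procedures before Day 238, so the split should not be tied to that day.
- Use subjects who received the dose as the denominator, give person-time for follow-up, and keep a whole-study total column so that nothing is lost.

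At minimum, add 28- and 7-day versions of the serious-event (SOC and PT) and AESI by-dose tables.

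The cost is a wording change in section 9.1 and one period variable built from dates already collected. The downside is one or two extra columns per table.
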